10.1.1 DEFINITION OF BASELINE AND CHANGE FROM BASELINE

Baseline for each parameter is defined as the last value measured prior to dosing, including repeat (vital signs) and unscheduled predose readings (see Section 10.1.2 for definitions of repeat and unscheduled readings).

For safety data, mean change from baseline is the mean of all individual subjects' change from baseline values. Each individual change from baseline will be calculated by subtracting the individual subject's baseline value from the value at the time point. The individual subject's change from baseline values will be used to calculate the mean change from baseline using a SAS procedure such as Proc Univariate.

10.1.2 REPEAT AND UNSCHEDULED READINGS

Repeat readings occur when the original vital signs or ECG result requires confirmation. Repeat readings are labelled as 'Repeat' in the listings and replace the original readings in all summaries and changes from baseline presentations and calculations. Prior to dosing, all readings taken in addition to the original reading are defined as predose repeats. Postdose repeat readings are defined as readings collected within 15 minutes of the actual time of the original reading.

With the exception of predose results described above, unscheduled readings for vital signs or ECGs are defined as readings collected >15 minutes from the actual time of the original reading. All results not taken at a scheduled time point for other data types (eg, clinical laboratory parameters) are unscheduled. Unscheduled readings are labeled as 'Unscheduled' in the listings. Because unscheduled postdose readings are not associated with any scheduled time point, they are excluded from all summaries.

10.2 Demographics and Subject Disposition

The demographic variables age, sex, race, ethnicity, body weight, height, and body mass index (BMI) will be summarized and listed. Subject disposition will be summarized and listed.

10.3 Pharmacokinetic Assessment

10.3.1 Pharmacokinetic Analysis

For each subject, the following PK parameters will be calculated, whenever possible, based on the concentrations of BVD-523, BVD-0513A, and BVD-0502A+BVD-0503A in plasma and

concentrations of total radioactivity in plasma and whole blood, using noncompartmental methods performed using Phoenix WinNonlin (Certara USA, Inc.) Version 6.4 or higher:

Parameter	Definition
C_{\max}	maximum observed concentration
T_{\max}	time to maximum concentration
AUC_{0-t}	area under the concentration-time curve calculated using the linear trapezoidal rule from Hour 0 to the last measurable concentration
AUC_{0-12}	area under the concentration-time curve calculated using the linear trapezoidal rule from Hour 0 to Hour 12
AUC_{0-24}	area under the concentration-time curve calculated using the linear trapezoidal rule from Hour 0 to Hour 24
$AUC_{0-\infty}$	area under the concentration-time curve extrapolated to infinity, calculated using the formula: $AUC_{0-\infty} = AUC_{0-t} + \frac{C_t}{\lambda_z}$ where C_t is the last measurable concentration and λ_z is the apparent terminal elimination rate constant
% AUC_{extrap}	percentage of $AUC_{0-\infty}$ determined by extrapolation
λ_z	apparent terminal elimination rate constant, where λ_z is the magnitude of the slope of the linear regression of the log concentration versus time profile during the terminal phase
$t_{1/2}$	terminal phase half-life, where $t_{1/2} = \text{natural log}(2)/\lambda_z$
CL/F	apparent oral clearance (for BVD-523 only)
V_z/F	apparent volume of distribution (for BVD-523 only)
$AUC_{0-\infty}$ Blood /Plasma Ratio	$AUC_{0-\infty}$ of total radioactivity in whole blood/ $AUC_{0-\infty}$ of total radioactivity in plasma
$AUC_{0-\infty}$ Plasma BVD-523/ Total	$AUC_{0-\infty}$ of nonradiolabeled BVD-523 in plasma/ $AUC_{0-\infty}$ of total

Radioactivity Ratio	radioactivity in plasma
AUC ₀₋₁₂ Blood/Plasma Total Radioactivity Ratio	AUC ₀₋₁₂ of total radioactivity in whole blood/AUC ₀₋₁₂ of total radioactivity in plasma
AUC ₀₋₁₂ Plasma BVD-523/ Total Radioactivity Ratio	AUC ₀₋₁₂ of nonradiolabeled BVD-523 in plasma/AUC ₀₋₁₂ of total radioactivity in plasma
AUC ₀₋₂₄ Blood/Plasma Total Radioactivity Ratio	AUC ₀₋₂₄ of total radioactivity in whole blood/AUC ₀₋₂₄ of total radioactivity in plasma
AUC ₀₋₂₄ Plasma BVD-523/ Total Radioactivity Ratio	AUC ₀₋₂₄ of nonradiolabeled BVD-523 in plasma/AUC ₀₋₂₄ of total radioactivity in plasma
AUC _{0-∞} Plasma Metabolites/ Total Radioactivity Ratio	AUC _{0-∞} of nonradiolabeled metabolites in plasma/AUC _{0-∞} of total radioactivity in plasma
AUC ₀₋₁₂ Plasma Metabolites/ Total Radioactivity Ratio	AUC ₀₋₁₂ of nonradiolabeled metabolites in plasma/AUC ₀₋₁₂ of total radioactivity in plasma
AUC ₀₋₂₄ Plasma Metabolites/ Total Radioactivity Ratio	AUC ₀₋₂₄ of nonradiolabeled metabolites in plasma/AUC ₀₋₂₄ of total radioactivity in plasma

In addition, the following PK parameters will be calculated, whenever possible, for each subject based on the urine concentrations of BVD-523 and total radioactivity. Parameters for BVD-523 in urine will be calculated and reported by the Covance EC Biometrics PK group; parameters for total radioactivity (except CL_R, which will be calculated for BVD-523 only) will be calculated and reported by the Covance Radioanalysis group. Urinary parameters for total radioactivity will also be presented in the CSR tables.

Parameter	Definition
A_{eu}	amount excreted in urine over sampling interval (t1-t2) where t1 and t2 are the start and end times of the sampling interval, respectively
Cumulative A_{eu}	cumulative amount excreted in urine, calculated as the sum of the amount excreted in urine for each collection interval
CL_R	renal clearance, where $CL_R = A_{eu}/AUC_{0-\infty}$ (for BVD-523 only)
% F_{eu}	percent of dose excreted in urine over sampling interval (t1-t2), where % Excreted = $100 (A_{eu}/\text{dose})$
Cumulative % F_{eu}	cumulative percent of dose excreted in urine, calculated as the sum of the percent of dose excreted in urine for each collection interval

The following PK parameters will be calculated, whenever possible, for each subject based on the fecal concentrations of total radioactivity. Parameters for total radioactivity will be reported by the Covance Radioanalysis group in the Radioanalysis report. Fecal parameters for total radioactivity will also be presented in the CSR tables.

Parameter	Definition
A_{ef}	amount excreted in feces over sampling interval (t1-t2)
Cumulative A_{ef}	cumulative amount excreted in feces, calculated as the sum of the amount excreted in feces for each collection interval
% F_{ef}	percent of dose excreted in feces over sampling interval (t1-t2), where % Excreted = $100 (A_{ef}/\text{dose})$
Cumulative % F_{ef}	cumulative percent of dose excreted in feces, calculated as the sum of the percent of dose excreted in feces for each collection interval

Additional PK parameters may be determined where appropriate.

Pharmacokinetic analysis will, where possible, be carried out using actual postdose times recorded in the raw data. If actual times are missing, nominal times may be used with sponsor approval.

Concentrations are used as supplied by the analytical laboratory for PK analysis. The units of concentration and resulting PK parameters, with amount or concentration in the unit, will be presented as they are received from the analytical laboratory.

C_{\max} and T_{\max} will be obtained directly from the plasma concentration-time profiles.

For multiple peaks, the highest postdose concentration will be reported as C_{\max} . In the case that multiple peaks are of equal magnitude, the earliest T_{\max} will be reported.

The amount excreted in urine (A_{eu}) for each urine collection interval will be calculated as the product of urine concentration and urine weight; Cumulative A_{eu} 0-x hour will be calculated by summing the A_{eu} values for each collection interval over the 0-x hour period.

In addition to the PK and radioanalysis results, a discussion of the results of metabolite characterization will be included in the CSR however no tables, figures, or listings will be generated. The quantitation of parent and metabolites (concentrations and/or percent of dose), as applicable, other applicable metabolite characterization results (representative chromatograms, proposed metabolite structures, etc.), and any PK parameters calculated from the radiochromatography data will be reported in the Metabolite Profiling and Identification report. Radiochromatography PK parameters may be summarized in the CSR along with PK parameters determined from the bioanalytical data.

10.3.1.1 Criteria For Handling Concentrations below the Limit of Quantification in Pharmacokinetic Analysis

Concentration values that are below the lower level of quantification (BLOQ) will be set to zero, with defined exceptions as follows;

- Any embedded BLOQ value (between 2 quantifiable concentrations) and BLOQ values following the last quantifiable concentration in a profile will be set to missing for the purposes of PK analysis.
- If there are late positive concentration values following 2 BLOQ concentration values in the apparent terminal phase, these values will be evaluated. If these values are considered to be anomalous, they will be set to missing.

- If an entire concentration-time profile is BLOQ, the profile will be excluded from the PK analysis.
- If a predose concentration is missing, this value may be set to zero with sponsor approval.

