The emerging AE profile is revealing that events related to the skin and gastrointestinal tract are particularly common, as are the general disorders of fatigue, edema, and fever. Adverse events related to skin, pruritus and rash, have been common, although other less common but significant skin events have also been reported, including erythema multiforme, light sensitivity, and keratoacanthoma. Rash has been managed with topical and/or oral concomitant medications and dose interruptions and/or reductions as necessary. The gastrointestinal events of nausea, vomiting, and diarrhea have been observed commonly, in some cases occurring in association with dehydration and elevated creatinine and renal insufficiency. Nausea, vomiting, and diarrhea have been managed with study drug dosing interruptions (and/or dose reductions) and supportive medications as needed. The general events of fatigue, edema, and fever have also been managed variably with supportive medications and/or interruption of study drug administration until improvement or resolution.

Study drug-related events of elevated aspartate aminotransferase and/or ALT and elevated creatinine, while not common, have been reported and have been managed with study drug interruption and, in some instances, dose reduction or discontinuation. Other possibly related or related AEs of particular interest include ocular effects, cardiac failure, thrombotic thrombocytopenia purpura, effects on peripheral blood counts, and photosensitivity.

BVD-523 has, to date, been administered to adult patients and has not been administered in conjunction with other anti-neoplastic agents with the exception of hydroxyurea (allowed short-term in the MDS/AML study) and hormonal therapy.

Orally administered BVD-523 at doses ranging from 10 to 900 mg BID was generally slowly absorbed in patients with advanced malignancies, with individual time to maximum concentration (T_{max}) values of 2 to 8 hours at dose levels of 10 to 150 mg BID, and median T_{max} values of 3 to 4 hours at dose levels of 300 to 900 mg BID. After reaching C_{max} , plasma BVD-523 concentrations remained somewhat sustained for

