approximately 2 to 4 hours. The compound half-life ranges from 9 to 11 hours. Exposure (C_{\max} and AUC_{0-12}) to BVD-523, as well as selected metabolites, generally increased in a dose-related fashion from dose levels of 10 to 600 mg BVD-523 BID. At Day 1, a further increase in exposure was seen at 750 mg BVD-523 BID, but exposure was similar between 750 and 900 mg BID. At Day 15, no further increase in exposure was observed as the dose increased from 600 to 900 mg BVD-523 BID.

A single-dose, 2-way crossover study to evaluate the effects of food on the pharmacokinetics (PK), safety, and tolerability of an orally administered 600-mg dose of BVD-523 has been completed in healthy volunteers. Fourteen healthy volunteers were dosed in this study. Following single-dose oral administration of 600 mg BVD-523, the median T_{\max} occurred at 3.1 hours in fasted subjects and at 6.1 hours in fed subjects (high-fat breakfast). Overall, a total of 6 treatment-emergent AEs (TEAEs) were reported in 5 subjects (35.7%). There were no deaths or serious AEs (SAEs) reported during the study and no TEAEs that led to discontinuation of subjects. All TEAEs were transient and had resolved by the end of the study.

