^h Single oral dose of [¹⁴C]-BVD-523 at 600 mg (approximately 200 µCi) administered orally after a 2-hour fast that follows breakfast.

ⁱ Blood samples for PK and radioanalysis collected at 0 Hour (predose); 30 minutes postdose; and 1, 2, 3, 4, 5, 6, 8, 12, 24, 48, 72, 96, 120, 144, and 168 hours postdose (Day 8). If subject is not discharged on Day 8, additional blood samples will be collected for radioanalysis every 24 hours until Discharge.

^j Blood samples for metabolite profiling and identification collected at 0 Hour (predose); 30 minutes postdose; and 1, 2, 3, 4, 5, 6, 8, 12, 24, 48, 72, 96, 120, 144, and 168 hours postdose (Day 8).

^k Urine samples collected at -12 to 0 (predose, the last void within 1 hour prior to dosing), 0 to 6, 6 to 12, and 12 to 24 hours postdose; and 24-hour intervals until Discharge.

^l Fecal samples collected predose (within 24 hours of dosing, if possible), from 0 to 24 hours postdose, and 24-hour intervals until Discharge.

^m Any SAEs occurring after the subject signs the Informed Consent Form will be collected.

ⁿ Subjects will be monitored for AEs beginning at initiation of study drug. An AE inquiry will be performed at Check-in and at each postdose vital sign measurement.

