7.3 Pharmacokinetic Analysis

For each subject, the following PK parameters will be calculated, whenever possible, based on the plasma concentrations of BVD-523, metabolites, and total radioactivity in whole blood and plasma, according to the model independent approach³:

C_{\max}	maximum observed concentration
T_{\max}	time to maximum concentration
AUC_{0-t}	area under the concentration-time curve calculated using the linear trapezoidal rule from Hour 0 to the last measurable concentration

AUC ₀₋₁₂	area under the concentration-time curve calculated using the linear trapezoidal rule from Hour 0 to Hour 12
AUC ₀₋₂₄	area under the concentration-time curve calculated using the linear trapezoidal rule from Hour 0 to Hour 24
AUC _{0-∞}	area under the concentration-time curve extrapolated to infinity, calculated using the formula: $AUC_{0-\infty} = AUC_{0-t} + \frac{C_t}{\lambda_z}$ where C _t is the last measurable concentration and λ _z is the apparent terminal elimination rate constant
% AUC _{extrap}	percentage extrapolation
λ _z	apparent terminal elimination rate constant, where λ _z is the magnitude of the slope of the linear regression of the log concentration versus time profile during the terminal phase
t _{1/2}	terminal phase half-life, where t _{1/2} = natural log (2)/λ _z
CL/F	apparent oral clearance (for BVD-523 only)
V _z /F	apparent volume of distribution (for BVD-523 only)
AUC _{0-∞} Blood/Plasma Ratio	AUC _{0-∞} of total radioactivity in whole blood/AUC _{0-∞} of total radioactivity in plasma
AUC _{0-∞} Plasma BVD-523/Total Radioactivity Ratio	AUC _{0-∞} of nonradiolabeled BVD-523 in plasma/AUC _{0-∞} of total radioactivity in plasma
AUC ₀₋₁₂ Blood/Plasma Ratio	AUC ₀₋₁₂ of total radioactivity in whole blood/AUC ₀₋₁₂ of total radioactivity in plasma
AUC ₀₋₁₂ Plasma BVD-523/Total Radioactivity Ratio	AUC ₀₋₁₂ of nonradiolabeled BVD-523 in plasma/AUC ₀₋₁₂ of total radioactivity in plasma
AUC ₀₋₂₄ Blood/Plasma Ratio	AUC ₀₋₂₄ of total radioactivity in whole blood/AUC ₀₋₂₄ of total radioactivity in plasma
AUC ₀₋₂₄ Plasma BVD-523/Total Radioactivity Ratio	AUC ₀₋₂₄ of nonradiolabeled BVD-523 in plasma/AUC ₀₋₂₄ of total radioactivity in plasma
AUC _{0-∞} Plasma Metabolites/Total Radioactivity Ratio	

$AUC_{0-\infty}$ of nonradiolabeled metabolites in plasma/ $AUC_{0-\infty}$
of total radioactivity in plasma
 AUC_{0-12} Plasma Metabolites/Total Radioactivity Ratio
 AUC_{0-12} of nonradiolabeled metabolites in plasma/ AUC_{0-12}

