4. INTRODUCTION

This SAP has been developed after review of the clinical study protocol (Final 2.0 dated 07 December 2016).

This SAP describes the planned analysis of the safety, tolerability, metabolism and PK data from this study. A detailed description of the planned TFLs to be presented in the Clinical Study Report (CSR) is provided in the accompanying TFL shell document.

The intent of this document is to provide guidance for planned analysis of the safety, metabolism, and PK data. In general, the analyses are based on information from the protocol, unless they have been modified by agreement between BioMed Valley Discoveries Inc. and Covance Early Clinical (EC) Biometrics. A limited amount of information concerning this study (eg, objectives, study design) is given to help the reader's interpretation. This SAP must be finalized prior to the lock of the clinical database for this study. When the SAP and TFL shells are agreed upon and finalized, they will serve as the template for this study's CSR.

This SAP supersedes the statistical considerations identified in the protocol; where considerations are substantially different, they will be so identified. If additional analyses are required to supplement the planned analyses described in this SAP, they may be performed and will be identified in the CSR. Any substantial deviations from this SAP will be agreed upon between BioMed Valley Discoveries Inc. and Covance EC Biometrics and identified in the CSR.

This SAP is written with consideration of the recommendations outlined in the International Conference on Harmonisation (ICH) E9 guideline entitled, "Guidance for Industry: Statistical Principles for Clinical Trials" and the ICH E3 guideline entitled, "Guidance for Industry: Structure and Content of Clinical Study Reports."^{1,2}

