10.3.1.2 Criteria for the Calculation of an Apparent Terminal Phase Half-Life

- **Number of Data Points**

- At least 3 data points will be included in the regression analysis and preferably should not include C_{\max} .

- **Goodness of Fit**

- When assessing terminal phases, the R^2 adjusted value will be used as a measure of the goodness of fit of the data points to the determined line.
- An terminal phase half-life will only be calculated if the R^2 adjusted value of the regression line is greater than or equal to 0.7.

- **Period of Estimation**

- Time period used for the estimation of apparent terminal phase half-lives, where possible, will be over at least 2 half-lives.
- Where an elimination half-life is estimated over a time period of less than 2 half-lives, it will be flagged in the data listings at the discretion of the Pharmacokineticist, and the robustness of the value should be discussed in the study report.

- **Calculation of AUC**

- The minimum requirement for the calculation of AUC will be the inclusion of at least 3 consecutive plasma concentrations above the lower limit of quantification (LLOQ), with at least 1 of these concentrations following C_{\max} . Exceptions may be made for metabolites.
- For any partial AUC determination (ie, AUC_{0-12} and AUC_{0-24}), nominal time will generally be used for the end of the interval. Actual times for partial AUC intervals may be used at the discretion of the Pharmacokineticist.

- $AUC_{0-\infty}$ values where the percentage extrapolation is less than 20% will be reported. $AUC_{0-\infty}$ values where the percentage extrapolation is 20% to 30% will be flagged and included in the descriptive statistics, whilst $AUC_{0-\infty}$ values where the percentage extrapolation is greater than 30% will be reported but excluded from descriptive statistics.

- **Anomalous Values**

- If a value is considered to be anomalous due to being inconsistent with the expected PK profile, it may be appropriate to exclude this point from the PK analysis based on the Covance SOP. However, the exclusion of data must have strong justification and will be documented in the raw data and study report.
- Positive predose value(s) greater than 5% of C_{max} may be excluded from the summary statistics of PK tables and statistical analysis at the discretion of the Pharmacokineticist and BioMed Valley Discoveries Inc.

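### If BVD-523 stays quantifiable to 48 h or later, the linear trapezoidal rule overstates its AUC0-t and AUC0-∞ by about 4–7%; linear-up/log-down would largely remove this

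*SAP*

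**What the plan says.** SAP 10.3.1 defines AUC0-t as the "area under the concentration-time curve calculated using the linear trapezoidal rule from Hour 0 to the last measurable concentration" and applies the same rule to AUC0-12 and AUC0-24. Protocol 7.3 matches it; its AUC0-24, for example, is the "area under the concentration-time curve calculated using the linear trapezoidal rule from Hour 0 to Hour 24". In both documents AUC0-∞ is AUC0-t plus Ct/λz, so it inherits any error in AUC0-t. Neither document provides a logarithmic rule for the declining part of the profile.

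The blood-sampling footnote to Protocol Table 6-1 has frequent samples up to 6 h and then "8, 12, 24, 48, 72, 96, 120, 144, and 168 hours postdose (Day 8").

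Protocol 2.1.2 says, of patients on twice-daily dosing: "The compound half-life ranges from 9 to 11 hours". In healthy volunteers given a single 600 mg dose, median Tmax "occurred at 3.1 hours in fasted subjects and at 6.1 hours in fed subjects". Neither document states an assay LLOQ or an expected last quantifiable time.

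**The concern.** The linear rule joins neighbouring samples with a straight line. Across an exponential decline that line lies above the curve, and the excess grows with the number of half-lives between samples. Here the gaps widen to 12 h and then 24 h just where BVD-523 is expected to be falling with a half-life of 9–11 h.

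Pharmacokinetics is part of the primary objective. AUC0-∞ is the denominator of CL_R by the documents' own formula, and of CL/F and Vz/F by their usual definitions, so an inflated AUC0-∞ lowers all three. The extrapolation rule in SAP 10.3.1.2 would not reveal this: when the last quantifiable sample is at 48 h or later only a few percent of the area is extrapolated, and the affected values pass unflagged.

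**Working it through.** The plan states no figure for AUC accuracy, so there is nothing of its own to reproduce. The size follows from its sampling times and its PK background.

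**Inputs.** Sampling times 0, 0.5, 1, 2, 3, 4, 5, 6, 8, 12, 24, 48 … 168 h (Protocol Table 6-1). Half-life 9, 10 and 11 h; Tmax 3.1 and 6.1 h (Protocol 2.1.2). Assumed: one-compartment oral profile, with ka solved from Tmax and the half-life.

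**Step 1, one gap.** For mono-exponential decline with rate k = ln 2/t½ over a gap d, linear area/true area = (kd/2)·coth(kd/2). At t½ = 10 h and d = 24 h, kd/2 = 0.8318, coth = 1.4675 and the ratio is 1.221.

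| t½ (h) | 12 h gap | 24 h gap |
|---|---|---|
| 9 | +7.0% | +27.0% |
| 10 | +5.7% | +22.1% |
| 11 | +4.7% | +18.4% |

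**Step 2, one full profile.** Take t½ 10 h, Tmax 3.1 h and F·dose/V = 1, so that true AUC0-∞ = 1/k = 14.427.
- 12–24 h: linear 12 × (0.4718 + 0.2054)/2 = 4.063, true 3.844; excess 0.219, or 1.52% of AUC0-∞.
- 24–48 h: linear 24 × (0.2054 + 0.0389)/2 = 2.932, true 2.402; excess 0.530, or 3.67%.
- All intervals before 12 h: −0.20%.
- Total with the last quantifiable sample at 48 h: 1.52 + 3.67 − 0.20 ≈ +5.0%.

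**Step 3, all six combinations (half-life × Tmax), true λz.**

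| Last quantifiable sample | Linear AUC0-∞ | Linear AUC0-t |
|---|---|---|
| 48 h | +4.45 to +5.88% | +4.70 to +6.08% |
| 72 h | +5.20 to +6.64% | +5.26 to +6.67% |
| 168 h | +5.41 to +6.78% | +5.41 to +6.78% |

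With λz regressed on the last three points, the 48 h row for AUC0-∞ becomes +4.45 to +5.95%. Linear-up/log-down on the same samples gives about −0.3 to −0.8%.

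**Step 4, other shapes, 48 h or later.** A 2–4 h plateau after Cmax, as Protocol 2.1.2 describes, gives about +5.0 to +7.1%. Bi-exponential decline (assumed first-phase half-life 2–4 h, first-phase weight 0.3–0.7, ka 1/h, terminal half-life 9 or 11 h) gives +4.0 to +6.4%. Hence about 4–7% overall. A longer half-life shrinks the one-compartment error: +2.8 to +4.1% at an assumed 15 h and +1.6 to +2.8% at 20 h.

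**Step 5, clearance.** 1 − 1/1.0445 = 4.3% and 1 − 1/1.0678 = 6.3%. Vz/F moves by the same proportion, because λz does not depend on the AUC rule.

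**Step 6, what 48 h requires.** C(48 h)/Cmax is 0.035 to 0.088, so the LLOQ must be at or below about 3.5–9% of Cmax. The extrapolated share is then 2.6–5.7%.

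**Step 7, last quantifiable sample at 24 h.** One compartment, true λz: +0.7 to +1.7%. With λz regressed on 8, 12 and 24 h at Tmax 6.1 h: +3.7 to +4.2%, most of it from λz. Bi-exponential: −1.9 to +1.2%. For one such profile (half-lives 4 and 11 h, equal weights), linear gives −1.3% and log-down −3.2%.

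**Step 8, partial AUCs and ratios.** Linear AUC0-24 is +1.1 to +2.0%, and AUC0-12 is −0.3 to −0.6%. For the parent/total-radioactivity AUC0-∞ ratio I assume parent half-life 10 h, metabolite half-lives 20 or 40 h, parent quantifiable to 48 h or later and radioactivity to 168 h. The error is +1.6 to +4.2% at an assumed 20% parent share, +1.0 to +3.1% at 40% and +0.3 to +2.1% at 60%, against −0.4 to −1.3% with log-down. The AUC0-24 ratio is +0.3 to +1.1%, and the AUC0-12 ratio is within 0.2%.

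**The case against.** The strongest reply is that this is a method preference. Protocol and SAP prespecify the same rule, the study is descriptive with six subjects, and no hypothesis is tested. The documents give no between-subject variability. At an assumed CV of 20–40% the standard error of a mean is 20/√6 to 40/√6, or about 8–16%, which is larger than the bias. That stands as a limit on importance. It does not remove the point, because where the conditions hold the bias runs the same way in every subject and can be avoided.

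The size is conditional, and this also stands. It needs an LLOQ that the documents do not give, and it carries a half-life from patients on repeated dosing over to healthy men after one dose.

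A reader might infer that the error is always upward, so that averaging over subjects can never remove it, or that it is a dependable 1–2% when plasma is quantifiable only to 24 h. The documents support neither. SAP 10.3.1.2 has λz estimated by regression, and with that the 24 h error runs from −1.9% to +4.2% depending on shape. In most bi-exponential cases log-down is no better or slightly worse. The SAP already covers part of this case: "values where the percentage extrapolation is 20% to 30% will be flagged and included in the descriptive statistics", and values above 30% are left out of the summaries. Five of the six one-compartment 24 h scenarios fall in the flagged band.

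Comparability with earlier BVD-523 studies is a fair worry. The documents do not say which rule those studies used.

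**Conclusion.** The point holds in conditional form, as a cheap improvement. If BVD-523 is quantifiable to 48 h or later and its terminal half-life is near 9–11 h, the planned rule overstates AUC0-t and AUC0-∞ by about 4–7%, and CL/F, CL_R and Vz/F read about 4–6% low. If the half-life is longer, the error is smaller. If BVD-523 is quantifiable only to 24 h, there is no reliable gain from changing the rule.

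The reach is limited. AUC0-12, AUC0-24 and their ratios move by no more than about 2%. The parent/total-radioactivity AUC0-∞ ratio is only partly affected, because total radioactivity contains the parent and part of the error cancels. Mass balance and metabolite identification do not use AUC. A reader might also take this for a conflict between Protocol and SAP, or for a threat to the primary objective. It is neither: the two documents agree, and the issue is the accuracy of a few reported parameters.

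**What to change.** In SAP 10.3.1, define the AUCs by linear-up/log-down, with the same rule for BVD-523, the metabolites and total radioactivity so that the ratios stay consistent. Keep the linear-rule AUCs as a listing for comparison with earlier studies. Record the departure from Protocol 7.3 in SAP section 12, which at present reports no changes. SAP section 4 allows this: the SAP supersedes the protocol's statistical considerations, and "where considerations are substantially different, they will be so identified".

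The cost is one WinNonlin setting, revised AUC definitions, one entry in section 12 and one extra listing, all before database lock. No further samples or visits are needed. The downside is that the main tables may follow a different rule from earlier studies, which the listing largely covers.
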